 - For participants who are in Group 2, materials should be placed in a Blue folder in order to avoid confusion as to which group they are. For Lovejoy Surgicenter, randomization envelopes will also be marked with Blue ink to correspond.

• **III. FLOW DIAGRAM OF STUDY PROCEDURES**

Flow Diagram Continued

IV. ASSESSING STUDY ELIGIBILITY AND PARTICIPANT ENROLLMENT

A. Beginning the Screening Process

For the purposes of this study, a screened patient will be defined as one who was identified based on gestational age and procedure type (D&E), as being potentially eligible for the study and who was approached about study participation.

B. Assessing interest in study participation

Once staff have identified a patient who might be eligible, based on patient age, gestational age and procedure type, for study participation, study staff should approach the patient to gauge interest in participating in the study. Research staff should assess the patient's interest in study participation by describing the study using the following study description. This study description is also printed on the Recruitment Script Form. Please adapt as needed.

Digoxin RCT Recruitment Script

Digoxin RCT Recruitment Script

Hi my name is _____ and I am a researcher. I am working on a study that you are eligible for, is it okay if I tell you a little bit about it? It is totally optional, so after you hear about it, it will be up to you to decide if you're interested in being in the study.

The study is on a medication called digoxin. Digoxin is FDA approved to treat heart conditions, but it is often used before abortions to stop the fetal heart from beating. In some clinics, all women who are having an abortion after 20 weeks of gestation receive digoxin, and in some clinics they don't use this medication at all. Some doctors think that using digoxin helps to make the abortion procedure faster and easier, but we don't know this for sure. That is why we're studying digoxin; we want to know if using digoxin makes the abortion faster, easier and safer.

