6. Ask the patient if they took any medication for nausea since leaving the clinic yesterday. If they have taken any medications for nausea since leaving the clinic yesterday, check “Yes” and print the medication name. If they haven’t taken any other medications, check “No”.
 7. Ask the patient if they called the clinic for any reason since leaving the clinic yesterday. If they have called the clinic check “Yes” and print the reason for their call. If they haven’t taken any other medications, check “No”.
 8. Ask the patient if they went to an Emergency Room or any other clinic for any reason since leaving the clinic yesterday. If they did go to an Emergency Room or another clinic check “Yes” and print the reason for their visit. If they haven’t taken any other medications, check “No”.
 9. Ask the patient what their bleeding has been like since leaving the clinic yesterday. Read them the question as printed followed by the following 4 responses: “No bleeding”, “Spotting or light bleeding only”, “Moderate bleeding (like a period)”, or “Heavy bleeding (heavier than a bleeding)”. Tick the appropriate response.
 10. Ask the patient if they noticed the fetus had stopped moving?. If they say yes, check “Yes” and record the approximate time they last felt fetal movement if they can remember. Record the time in 12hr format, as hh:mm and circle AM or PM. If they don’t remember, write “99:99”. If they have not felt any stop in fetal movement, check “No”.
 11. Ask the patient which medication they think they received yesterday. Check the appropriate response and write why they think they received that particular medication. If the participant cannot offer a guess of which medication she received check “Don’t Know”.
 12. Ask the patient to assess her pain currently on a scale of 0-10. Show her the 0-10 scale on Form 3 and read the question as printed on the Form. Ask her to select the appropriate box on the scale. Mark an “X” in the appropriate box, based on her response.
 13. Ask the patient how acceptable this amount of pain was to her. Read the 5 response choices to the patient: “Very acceptable”, “Somewhat

Acceptable", "Somewhat Unacceptable", or "Very Unacceptable". Tick the appropriate response. If the patient is unable to answer the question, tick "Don't know".

14. After the patient questionnaire is completed, refer to the patient's medical chart. Check "yes" or "no" to reflect whether misoprostol was given adjunctively.

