- a. If checked "Yes", provide the time in HH:MM (12hr format) and circle AM or PM. Record the dose in *micrograms* and report the route of drug delivery by checking "Buccal", "Oral" or "Other". If choosing other record the route used.

15. Check "yes" or "no" to reflect whether the patient was given any other medications after arrival at the clinic and before the procedure (like ibuprofen, morphine, Zofran, Ativan, norco, etc).

- a. If checked "yes", please list the medications given.

This is the end of **Form 3: Arrival Data, Day 2**. Upon completion of Form 3, study staff should:

- Review Form 3 for accuracy and completeness
- Make corrections as necessary. Date and initial all corrections.
- Sign both sides of the Form in the header (next to "Staff signature")
- Proceed to **Form 4: Intra-operative Data, Day 2**, which must be completed during her abortion procedure.

D. Form 4: Intra-operative Data, Day 2

Form 4 Overview

Form 4 is used to document the initial pre-operative setup, procedure time, and details of the D&E procedure. Form 4 will also include the operating physician's assessment of procedure difficulty and his or her guess as to the study drug assignment. Questions from Form 4 should be completed in consultation with the operating physician. The operating physician must be listed on the Delegation of Authority Log as approved to perform the D&E.

Form 4 Detailed Instructions

1. Record today's date. Dates should be recorded as month/day/year (MM/DD/YYYY).
2. Print the last name of the clinician or physician performing the D&E on the line provided.
3. Record what anesthesia the patient received during their abortion procedure by checking the appropriate response.
 - a. Moderate sedation is defined as "a drug-induced depression of consciousness during which patients respond purposefully to verbal commands, either alone or accompanied by light tactile stimulation. No interventions are required to maintain a patent airway, and spontaneous ventilation is adequate. Cardiovascular function is usually maintained" per ASA guidelines

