4. Prior to the MD placing their speculum and starting to the procedure, the RN assisting with ultrasound during the procedure will check for fetal presentation and cardiac activity using the ultrasound. **The MD is blinded and CANNOT know whether or not cardiac activity is present. The study RA must remain blinded to cardiac activity as well.** The MD must be turned around and not looking at the ultrasound. The RN may inform the MD about fetal presentation but will not say whether or not there was cardiac activity aloud.

A separate log, the Cardiac Activity Log, will be used to record cardiac activity. RN will record the subject's enrollment ID, the date, cardiac activity (yes, no, or unsure) and initials. The Cardiac Activity Log will be kept in an opaque folder, and the research assistant will remain blinded to the cardiac activity.

5. Based on the findings of the RN performing the ultrasound, record the fetal presentation by ticking "Cephalic", "Breech" or "Transverse". If the fetal presentation is not listed in the response choices, tick "Other" and write in the fetal presentation on the line provided.

After the RN is done viewing cardiac activity, it may be necessary for the clinician to view the ultrasound during the procedure. This is acceptable as necessary for the procedure, however the physician should avoid intentionally searching for cardiac activity to the degree that is possible.

6. Using a clock, record the time when the speculum is first placed in the vagina. Record the time as standard time (12hr format) **hh:mm**. Circle AM or PM as appropriate. ***Start the stopwatch at this time.***
7.
 - a. The initial amount of cervical dilation will be measured using Bierers or ring forceps. Record which instrument the clinician uses to measure cervical dilation by checking either "ring forceps" or "Bierer forceps". (*Preference is ring forceps*)
 - b. The clinician will place the Bierers or ring forceps into the internal os of the cervix and open them as far as possible. The research assistant will use a paper ruler to measure the distance between the handles and will record the distance in **millimeters** in the spot marked "distance between handles".

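### Do the fetal-movement and drug-guess questions asked before the D&E undermine the masking of the Form 4 results?

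*Combined protocol and SAP*

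**What the plan says.** Form 3 (Section V.C) is completed when the woman arrives on Day 2. Item 10 is "Ask the patient if they noticed the fetus had stopped moving", with the time of last movement if she recalls it. Item 11 is "Ask the patient which medication they think they received yesterday", with her reason, and it allows a don't-know answer. The general instructions in Section V have staff read patient questions out as printed.

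The recruitment script (Section IV.B) has already told her that digoxin is a drug of which "it is often used before abortions to stop the fetal heart from beating", and that the placebo is salt water.

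After Form 3, study staff move on to Form 4, "which must be completed during her abortion procedure". The Form 4 overview (Section V.D) adds: "Questions from Form 4 should be completed in consultation with the operating physician". The explicit Day 2 masking rules are in Form 4 item 4 and concern the ultrasound finding: "The MD is blinded and CANNOT know whether or not cardiac activity is present" and "The study RA must remain blinded to cardiac activity as well". The nurse's finding goes into a separate log in an opaque folder. The text after item 5 accepts that "it may be necessary for the clinician to view the ultrasound during the procedure".

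Section IX names operative time as the primary endpoint, and ease of procedure, achievement of fetal demise and complications as secondary endpoints.

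**The concern.** The SOP guards cardiac activity closely. Minutes or hours earlier, its own staff elicit a proxy for the same fact and write it down. A woman who felt movement stop, and who knows what digoxin does, may well say so. Form 3 hands staff straight on to Form 4 and names no different recorder. Nothing in the supplied text seals the answers or bars passing them on, although the SOP writes such rules elsewhere: the Form 2 clinician questions are asked away from the patient, and drug containers stay out of the procedure room.

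Belief could matter here. The script says some doctors expect digoxin to make the procedure faster and easier, and Form 4 item 26 asks operators whether demise makes a D&E easier. A recorder or operator with that expectation could colour the timing or the difficulty rating. Form 3 records the woman's guess and Form 4 item 25 the operator's, but no item records the recorder's, so a leak to the recorder could not be examined afterwards.

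**Working it through.** **Step 1: who could learn the answers.**
- *Recorder.* Section V.C sends study staff from Form 3 to Form 4, and the research assistant takes the Form 4 measurements. One person doing both is not stated, but nothing rules it out. Take this route as open.
- *Operator.* No section places the operator at Form 3 or shows it to them. The consultation in the Form 4 overview is the physician supplying answers. The physician's judgement questions come after the physician is done with the patient, and item 16 has already stopped the stopwatch. That sentence is not a path by which Form 3 answers reach the operator before or during the case.

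**Step 2: which results an informed recorder could move.**

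| Form 4 item | How it is obtained | Section IX endpoint? |
|---|---|---|
| Times (items 6, 8, 10, 16) | Stopwatch never paused or reset; read at instrument entry, instrument removal and the end | Primary |
| Dilation by ruler (item 7) | Research assistant's measurement | No |
| Difficulty (item 21) | Physician's choice among four fixed options; may be written directly by the physician (Section V, rule 5) | Secondary (ease) |
| Cardiac activity (item 4) | Nurse's ultrasound finding, separate log | Secondary (demise) |
| Complications (item 17) | Named events, such as transfusion or perforation | Secondary |

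The softest recorder-dependent reading, the ruler, feeds no listed endpoint. The softest listed endpoint, difficulty, is not the recorder's judgement.

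**Step 3: how large a timing error would be needed.** Inputs: the target difference is 3 min = 180 s (Section IX, Sample size). Let d be the recorder's timing difference between believed-digoxin and believed-placebo cases, and g the between-arm difference in the proportion believed to be on digoxin. Belief is treated as two-valued; don't-know answers are ignored.

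Bias = d × g, so d = bias / g. Take 10% of the target as the smallest shift of interest: 0.10 × 180 = 18 s. The 10% and the values of g are assumptions.
- g = 0.2: d = 18 / 0.2 = 90 s per case
- g = 0.5: d = 18 / 0.5 = 36 s per case
- g = 0.8: d = 18 / 0.8 = 22.5 s per case

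**Step 4: what such a bias would do to the test.** The plan gives no SD. Solving its 86 per arm (two-sided alpha 0.05, 80% power, difference 3 min) for the SD gives 3 / [(1.960 + 0.842) × √(2/86)] = 7.02 min. With SD 7 min the normal approximation returns 86 per arm, 172 in total, which matches the plan. The standard error of the difference is then 7 × √(2/86) = 1.07 min. With no true effect, a bias of 0.25 min raises the two-sided rejection rate from 5% to 5.6%, and 0.5 min raises it to 7.5%. At g = 0.5 these need d = 15/0.5 = 30 s and 30/0.5 = 60 s in every case.

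No matching threshold can be set for difficulty, because the documents give no expected distribution of ratings. Exposure is at most 180 women, fewer once those not randomized or not returning are removed.

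**The case for a change.** The best argument for acting is that the SOP itself treats this kind of information as sensitive, no section uses the answers before or during the D&E, and one sentence would narrow the route. If the operator did learn the answer, the real conduct of the case or the difficulty rating could change, and Step 3 does not cover that: it bounds recorder error only. The operator's own guess at item 25, a check on blinding, could also be contaminated.

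Part of this stands. The text has no non-disclosure rule for items 10 and 11, and a leak to the recorder would leave no trace. But disclosure to the operator is conjecture on this text. The operator has a more direct source in any case, since the SOP allows them to look at the ultrasound when the case requires it.

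Stronger measures would gain little. Having the woman mark a card and sealing it until Form 4 is signed would need exceptions to the rules on staff completion, reading aloud and checking Form 3. It would leave weaker cues in the open (Form 3 also asks about nausea, vomiting, antiemetics and calls to the clinic) and would not stop a woman volunteering her belief. Moving item 11 after the D&E would be worse, because her guess would then be coloured by the procedure.

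**Conclusion.** No change to the plan follows. This is an unwritten detail that masked staff fill sensibly: people told to stay blind to cardiac activity have no reason to carry a woman's impression to the operator. Asking both items before the procedure is the right timing.

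Followed as written, the plan still gives sound results for operative time and ease. A recorder would have to mistime cases by 22.5 to 90 s according to belief to shift the primary comparison by a tenth of its target, which is hard to do at visible events on a running stopwatch. For ease, the rating belongs to the physician, and no stated step takes the Form 3 answers to that physician.

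The conclusion rests on the assumed range of g, on two-valued belief, and on staff not relaying the answers. It covers the supplied text only: the separate FDA Study Protocol, the printed forms and the Delegation of Authority Log were not available and may already settle the point. The actual bias cannot be estimated, because neither the gap in belief between arms nor any effect of belief on recording is given.

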Sample size was calculated for the primary outcome of procedure time. In order to detect at least a 3-minute difference in procedure time between groups with 80% power and alpha of 0.05 (using a 2-way test), we would need 172 patients, or 86 per arm. Loss to follow up only would occur if a subject was randomized, received the injection and dilators, then failed to return for her procedure. In order to account for this rare but possible situation, we intend to enroll a total sample of N=180 subjects.

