D. Assessing Exclusion criteria

Following inclusion criteria assessment, patients who are still eligible should be screened for exclusion criteria. These are assessed using *Items 8-17 of Form 1*

Exclusion Criteria: *(Items 8-17 Form 1)*

- Reason for abortion is fetal demise
- Participant has contraindications to digoxin including but not limited to:
 - o Known allergy to digoxin
 - o Current cardiomyopathy or impaired systolic or diastolic function
 - o History of heart attack
 - o Current pericarditis
 - o Any cardiac rhythm abnormalities
 - o Current heart disease of any other type
 - o Current uncontrolled thyroid disease (hypothyroidism or hyperthyroidism uncontrolled by medication)
 - o Acute or chronic renal failure
 - o Autoimmune renal disease
- Participant requires more than one day of cervical preparation
- Participant diagnosed with placenta accreta, increta or percreta
- Participant diagnosed with preterm premature rupture of membranes (PPROM)
- Participant diagnosed with anhydramnios
- Participant has active bleeding or is hemodynamically unstable
- Participant has signs of chorioamnionitis or any clinical infection (fever >100.4°F)

Eligibility must be confirmed by a clinician or physician and must be documented using **Form 1: Eligibility Screening and Baseline Data, Day 1**. Detailed instructions for completing Form 1 can be found in the section V. A. of these SOPs.

Women must meet ALL eligibility (both inclusion and exclusion) criteria to be considered eligible for this study. If a woman does not meet eligibility criteria she cannot participate in this study.

If a woman does meet ALL eligibility criteria (both inclusion and exclusion) and wishes to participate in the study, she is ready to be consented. However, inform the patient that her eligibility is only confirmed when she sees the clinician, so there is the possibility of her being consented and later found ineligible for the study based on the clinician's recommendations.

E. Administering study informed consent

The study Informed Consent Form (ICF) and HIPAA Consent Form (HCF) must be completed for all study participants. These forms must be signed and dated by the participant and an IRB approved study staff before any study procedures may take place.

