If a woman may be eligible for study participation and would like to participate in the study, she should be given an ICF and HCF to read and they should be explained to her. IF the woman cannot read the forms, then the forms should be read and explained to her. Study staff should ensure that the woman understands the requirements of the study protocol, the risks and benefits of the study participation, potential side effects and complications and the voluntary nature of the study participation. The woman should be given the opportunity to ask questions and to have them answered by the appropriate study staff.

If a woman agrees to participate in the study, she should sign and date the ICF and HCF. IRB-approved staff should also sign and date the ICF and HCF. Study staff should review the ICF and HCF to ensure that the patient has signed, the study staff has signed, and that both have written the correct date. If either the participant or study staff makes an error, she should cross out her mistake and clearly write the correction nearby. She should initial and date (MM/DD/YY) her correction.

The signed copies of the ICF and HCF should be kept by the study site. The patient should be offered copies of the ICF and HCF for her records. Furthermore ALL study participants should be given a copy of the Participant Bill of Rights.

Once the patient has signed the ICF and HCF, she is considered enrolled in the study. All enrolled participants should be asked to complete a records release form in the event that study staff need to request medical records from other institutions during the study period. After completion of the records release form, study staff should proceed with completing **Form 1: Eligibility and Baseline Info, Day 1**.

V. DATA COLLECTION

For this study, there are [5] data collection forms and an informed consent form. The [number] data collection forms are as follows:

- Form 1: Eligibility Screening Baseline Data, Day 1
- Form 2: Dilator and Injection Data, Day 1
- Form 3: Arrival Data, Day 2
- Form 4: Intra-operative Data, Day 2
- Form 5: Post-operative Data, Day 2

General Instructions for Data Collection Forms

1. All data collection forms should be completed thoroughly and carefully by an IRB-approved study staff using *black* ink. All five of the data collection forms should be completed for all study participants.

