 - Recruitment limits: maximum number of participants were enrolled for the day so no further patients approached; for SF or LJ, RA was only recruiting for one of the two gestational age groups and the

- participant was in the gestational age group that was not being recruited that day.
- Other: please write in parentheses what the reason for not approaching the patient.
 - Approached: record the *number* of participants that you approached. Each patient approached should have a corresponding data Form 1. Verify at the end of each day that the number of Form 1's completed matches the number "approached" recorded.
 - Declined: record the *number* of patients who declined to participate after you approached them about the study. For each participant that declines, ask the patient why they do not wish to participate. Record the reason(s) they provide for declining in the following column, separating each reason by a comma (ex: "don't want extra injection, don't want to spend extra time on study"). This response should also be documented on Form 1.
 - Determined ineligible after being approached: Based on their responses to Form 1 record the reason(s) the participant was found ineligible after being approached. These should also be recorded on Form 1. Ask the participant all of the eligibility questions regardless of eligibility status.
 - Enrolled: Record the number of participants enrolled for the day. Record the Enrollment ID of each participant enrolled under "Enrollment Numbers" column, separating each ID by a comma (SF001, SF002).
 - Randomized: Record the number of participants randomized for the day. If a participant was enrolled but not randomized (i.e. if # Enrolled ≠ # Randomized for the week) record the reason(s) for not being randomized, with each reason being separated by commas. The reason for not being randomized should also be recorded on Form 2. Reasons for not being randomized include ROM with dilator placement; patient withdrew from study before randomization; physician unable to complete injection; adverse event precludes patient completing study.

Enrollment Log

The enrollment log is used to track the progress of participants recruited for the study. In Column A, each row corresponds to a single participant.

- Date: Record the date that the participant was enrolled (Day 1)
- Enrollment ID: Record the participants Enrollment ID.

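### The target of 180 is set in enrolled women, meaning consent signed, while its 8-woman margin covers only loss after injection, so 80% power is not assured

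*Combined protocol and SAP*

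**What the plan says.** Section IX, Sample size, aims to detect a 3-minute difference in procedure time with 80% power and alpha 0.05, read here as two-sided. It concludes that "we would need 172 patients, or 86 per arm". It then describes the only loss it foresees: "Loss to follow up only would occur if a subject was randomized, received the injection and dilators, then failed to return for her procedure". To allow for that loss, "we intend to enroll a total sample of N=180 subjects".

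Section IV.E fixes what enrolment means: "Once the patient has signed the ICF and HCF, she is considered enrolled in the study".

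Other sections expect women to leave between that signature and randomisation:

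- Section IV.D tells staff to warn the patient that "there is the possibility of her being consented and later found ineligible" on the clinician's assessment.
- Section VI.A, Recruitment Log, has separate counts for enrolled and randomised women and an instruction that begins "If a participant was enrolled but not randomized". Its reasons are membrane rupture at dilator placement, withdrawal before randomisation, an injection that could not be completed, and an adverse event. The Enrollment Log repeats the first three.
- Section V.A gives each woman an Enrollment ID. Section V.B gives a separate Randomization ID.

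Section V.B also sets the point of randomisation by site. At Lovejoy it is the opening of the envelope, and that ID is spent even if no injection follows. At the San Francisco, Los Angeles and Long Beach sites it is the injection, and the number of a woman who withdraws earlier can be reused.

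**The concern.** The target is expressed in one unit (consents) and its allowance in another (randomised and injected women). The SOP itself names several causes of a gap between the two. The sample-size paragraph treats loss as possible only after injection, so it sets nothing aside for that gap.

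The gap follows from the workflow. Section V.B has the two FPAWH sites place dilators before the injection. A membrane rupture at dilator placement there happens after enrolment and before randomisation.

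If staff at the four sites take the SOP's definition at its word, recruitment could close at 180 consents with fewer than 172 operative times. The stated power would then be too high.

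**Working it through.** **Inputs from the documents.** Difference 3 minutes, power 80%, alpha 0.05 two-sided, 86 per arm, 172 in total, target 180 (all section IX).

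**Inputs not in the documents.** The SD of operative time, the rate of loss before randomisation and the rate of failure to return. These are assumptions below.

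**Step 1: the plan's own figure.** Without an SD, 172 cannot be reproduced independently. It can be back-solved for two independent means:

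SD = 3 × √(86/2) / (1.960 + 0.842) = 7.02 minutes.

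Forward with SD 7: n per arm = 2 × (1.960 + 0.842)² × 49 / 9 = 85.5, rounded up to 86. So 86 per arm fits an SD of about 7 minutes under the normal approximation. On the noncentral t, 86 per arm with SD 7 gives 79.8%.

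**Step 2: the allowance.** 180 − 172 = 8, and 8/180 = 4.4%. Check: 172 / (1 − 8/180) = 180. The arithmetic is sound.

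**Step 3: power if 180 means consents.** Let total loss be the share of the 180 without an operative time, whether lost before or after randomisation. The number analysed is 180 × (1 − loss). The last column is 172 / (1 − loss), rounded up.

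| Total loss (assumed) | Analysed | Power, two-sample t, SD 7 | Power, normal, SD 7.02 | Consents needed for 172 |
|---|---|---|---|---|
| 0% | 180 | 81.6% | 81.8% | 172 |
| 4.4% | 172 | 79.8% | 80.0% | 180 |
| 5% | 171 | 79.6% | 79.8% | 182 |
| 10% | 162 | 77.4% | 77.6% | 192 |
| 20% | 144 | 72.4% | 72.7% | 215 |

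The fourth column hardly depends on the SD. Once power is fixed at 80% for 172, the normal approximation gives power at N analysed as Φ(2.802 × √(N/172) − 1.960). For N = 162 this is Φ(2.719 − 1.960) = 77.6%.

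**Step 4: a less favourable split.** Suppose the full 8/180 fail to return and loss before randomisation comes on top. The number analysed is then 180 × (1 − pre-randomisation loss) × 172/180.

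- 5% not randomised: 171 randomised, 163 analysed, power 77.6%.
- 10%: 162 randomised, 155 analysed, power 75.5%.
- 20%: 144 randomised, 138 analysed, power 70.5%.

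These are two-sample t with SD 7.

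**Step 5: if 180 means randomised women.** Up to 8 can fail to return and 172 remain, so the plan's 80% stands. The consents needed to randomise 180 are 180/0.95 = 190, 180/0.90 = 200 and 180/0.80 = 225 at the same assumed rates.

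**The case against.** The strongest reply is that 180 was meant as randomised women. The loss sentence starts from a woman already randomised, and 180 is set to cover exactly that loss. Reuse of randomisation numbers at three sites, and the return of unopened Lovejoy envelopes, mean that a woman lost earlier leaves her place on the list open. On this reading the power statement holds with up to 8 no-shows. The reading is plausible, but it conflicts with the definition in section IV.E. Number reuse keeps the allocation list filled; it does not say when recruitment stops.

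A reader might go the other way and infer that the stated 80% is wrong, or that the trial will miss its 172. The documents do not support that. It needs recruitment to stop at 180 consents and combined loss to exceed about 4.4%, and neither is stated. Nor is there an arithmetic error: 2 × 86 = 172 and 172 + 8 = 180. The fault is in the unit being counted.

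Three further points stand in part:

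- The loss rates above have no source in the documents. The paragraph itself calls failure to return rare, so the split in step 4 may be pessimistic.
- At Lovejoy, a woman whose envelope is opened is randomised even without an injection. Withdrawal or a failed injection after that is not a route to non-randomisation, and she may still have an operative time.
- Section II.A lists a separate FDA Study Protocol in the study binder. It is not among the documents reviewed and may define the target.

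**Conclusion.** The target is ambiguous between consented and randomised women, and the SOP's own definition points to consents. On that definition the entire margin for all loss is 8 of 180 (4.4%), although the plan justifies those 8 by no-shows alone. Power of 80% is then not assured.

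The effect is negligible at 5% total loss. At 10% total loss power is about 2.4 points below the 79.8% given by 172 women, and at 20% about 7.4 points below. These sizes rest on a back-solved SD of 7 minutes, a comparison of two independent groups and assumed loss rates. The point deserves a correction because four sites recruit from this text and the correction is small.

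**What to change.** In section IX, Sample size, replace the enrolment target by one in randomised women: *randomize 180 women*. State that recruitment stops on the randomised count in the Recruitment and Enrollment Log.

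A bare count of Randomization IDs used would mix two rules, so add how each woman is counted: randomised by her own site's rule, which is envelope opened at Lovejoy and injection given at the other three sites. State also that women at Lovejoy whose envelope was opened but who received no injection stay in the intention-to-treat set.

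If 180 is instead meant as a cap on consents, say so, give an expected rate of loss before randomisation, and restate the expected evaluable number and the power it gives.

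The first option costs a few more consents, for example 190 instead of 180 if 5% of enrolled women are not randomised. The second costs a slightly less favourable stated power. Neither changes a clinical procedure or the analysis.
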